8.4 Analysis of CT data

The pre- and post SBRT +/- pembrolizumab CT scans will be assessed for HU density and f_{air} values as outlined in section 5.4.1. Baseline and post induction treatment values within patients will be assessed by the paired t-test. Comparison of the baseline and posttreatment values between the radiotherapy and radiotherapy + pembrolizumab arms will be assessed per time-point by the independent samples t-test.

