5.4.1 Quantitative changes in lung density

The aim of these measurements is to determine whether a relationship exists between SBRT dose and radiographic lung injury, as measured by CT density changes (70).

Contours of selected isodose levels (0.5 Gy, 3 Gy, 6 Gy, 12 Gy, 18 Gy, 24 Gy, 36 Gy, and 50 Gy) will be exported from the planning system along with the contours of the lung and internal target volume, and the average-intensity CT dataset. These isodose lines are chosen to provide a wide range of doses and large enough volumes between lines to allow for meaningful density measurements. This results in a total of eight evaluable dose-density regions in the ipsilateral lung. In the contralateral lung, only one dose-density region (receiving ≥ 3 Gy) will be analyzed, because it is uncommon for the contralateral lung to receive >5 Gy. The contralateral lung receiving <3 Gy will be considered unirradiated and as such used to correct for baseline differences between scanners. The regions receiving >50 Gy are not analyzed because these volumes are small and because small errors in registration can place a few millimeters of regressing or stable tumor within that volume, artificially increasing density measurements. After deformation of the follow-up scans, isodoses from the endinspiratory phase of the planning CT scan will then be overlaid on the deformed follow-up scan, and changes in Hounsfield unit (HU) density assessed.

The air-filled fraction (f_{air}) will be calculated from HU density using the formula $f_{\text{air}} = \frac{HU - NCT}{-1000 - NCT}$, where NCT is the CT number in HU (71). f_{air} represents the percentage of lung tissue that contains air, and it decreases with increasing CT density.

5.5 Ultrasound endoscopy guided cytological lymph node aspiration for immunological cell composition (EBUS FACS)

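### Section 5.4.1 sets out to relate CT density change to SBRT dose, but section 8.4 plans no test that uses dose and does not say how the several regions per patient are handled

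*Combined protocol and SAP*

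**What the plan says.** Section 5.4.1 (Quantitative changes in lung density) gives the purpose: "The aim of these measurements is to determine whether a relationship exists between SBRT dose and radiographic lung injury", with injury measured as CT density change. It lists eight isodose contours (0.5, 3, 6, 12, 18, 24, 36 and 50 Gy) and states: "This results in a total of eight evaluable dose-density regions in the ipsilateral lung". One further region is taken on the other side ("In the contralateral lung, only one dose-density region"), and the top of the range is cut off: "The regions receiving >50 Gy are not analyzed because these volumes are small". Contralateral lung below 3 Gy serves as an unirradiated reference to correct for scanner differences.

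Section 8.4 (Analysis of CT data) takes HU density and f_air "values as outlined in section 5.4.1" and names two tests. Within patients: "Baseline and post induction treatment values within patients will be assessed by the paired t-test". Between arms, baseline and post-treatment values are compared at each time-point by the independent samples t-test. No other section gives a regression, trend test, mixed model or dose covariate for these data.

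Section 5.2 plans 10 patients per arm and gives no power calculation. Section 3.3 has an explorative objective on radiation changes in the resected lobe; it does not mention CT density or dose.

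**The concern.** The measurement is built around dose and the analysis leaves dose out. A before-after test asks whether density changed. A between-arm test asks whether the arms differ. Neither asks whether the change is larger where the dose was larger, which is the question section 5.4.1 puts.

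The unit of analysis is also open. Each patient supplies several correlated values per scan, and averaging them, testing each region or combining them otherwise can give different answers. None of these is pre-specified, so the choice would be made with the data in hand. What is at stake is an exploratory analysis: the dose-resolved data would be collected, and a significant result under section 8.4 could be read as evidence of a dose relation when it is not.

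**Working it through.** **1. Aim against test**

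| | Section 5.4.1 | Section 8.4 |
|---|---|---|
| Question | Is density change related to dose? | Did density change? Do the arms differ at a time-point? |
| Data per patient and scan | Several dose regions | Not stated how regions enter |
| Role of dose | Defines the regions | None |

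This mismatch needs no assumption about variance.

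**2. Number of regions.** The bands between the eight contours are 0.5–3, 3–6, 6–12, 12–18, 18–24, 24–36 and 36–50 Gy: 8 − 1 = 7. With lung above 50 Gy excluded, eight regions exist only if ipsilateral lung below 0.5 Gy counts as one. Section 5.4.1 does not say so.

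**3. Does the paired t-test respond to dose?** The documents give no SD or effect size for HU, so these inputs are assumed: 20 patients, seven bands, a uniform +40 HU change with no dose relation, patient-level SD 20 HU and residual SD 20 HU. The SD of a patient's mean change is √(20² + 20²/7) = √457.1 = 21.4 HU. The standard error is 21.4/√20 = 4.78 HU, so the expected t is about 40/4.78 = 8.4. In 4,000 simulated trials the paired test was significant in 100%, and a test of the mean per-patient dose slope in 4.6% (nominal 5%). A significant paired test is therefore not evidence of a dose relation.

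**4. The region-by-region reading.** Testing each region separately at 0.05, with no multiplicity rule, gives at most 1 − 0.95⁸ = 34% familywise error for eight independent tests (30% for seven, 37% for nine). Regions in one patient are correlated. Simulated arm comparisons of 10 against 10 over eight bands gave about 30%, 25% and 20% at correlations 0.3, 0.5 and 0.7. A seven-band HU simulation with large shared baseline differences between patients gave 12%. The result is eight p-values and no trend estimate.

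**5. Would a dose slope also help the arm comparison?** Power for an arm effect with 10 per arm, eight bands and two-sided 0.05, at correlations 0.3 / 0.5 / 0.7 (effects and slope SDs in SD units, all assumed):

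| Arm effect | Between-patient slope SD | Slope contrast | Mean of all bands | Bonferroni by band |
|---|---|---|---|---|
| Linear, 0 to 1 SD | 0 | 65 / 79 / 95% | 40 / 29 / 23% | 41 / 38 / 31% |
| Linear, 0 to 1 SD | 0.5, lines spreading from lowest band | 53 / 64 / 78% | 36 / 27 / 22% | 35 / 30 / 25% |
| Linear, 0 to 1 SD | 1, lines spreading from lowest band | 35 / 39 / 45% | 26 / 21 / 19% | 22 / 18 / 16% |
| Linear, 0 to 1 SD | 1, lines pivoting at mid-range | 35 / 39 / 45% | 40 / 29 / 23% | 36 / 32 / 27% |
| Uniform, 1 SD | 0 | about 5% | 93 / 81 / 69% | not tabulated |

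Under the linear effect with no slope variation, a single t-test in the highest band has 56% power.

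On an HU scale (assumed baseline SD 40, patient shift SD 20, slope SD 40, residual SD 20; effect at 50 Gy of 80 against 140 HU) the slope contrast has 74% power. The all-region average has 16% on post-treatment values and 43% on change from baseline. With baseline and shift SDs of only 5 HU, the slope contrast has 74%, the post-treatment average 77% and the top band 82%. So the gain from a dose-by-arm contrast runs from none to large. Comparing change instead of each time-point helps where baseline differences between patients are large.

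**The case against.** Section 8.4 refers back to section 5.4.1, so its tests can be read as applying to each dose region in turn. A reader would then see whether the change grows from one band to the next. That is fair, and it means the dose question is not left wholly dark. It remains a descriptive gradient: no trend is estimated or tested, and no multiplicity rule is given. The scanner correction from low-dose contralateral lung does not supply a dose relation either.

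The trial is exploratory, section 5.2 disclaims a power calculation, and section 8.1 judges safety by grade 3 or higher pneumonitis. This limits the weight of the point; it does not give the stated aim an analysis.

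Two stronger readings are tempting. A reader might infer that section 8.4 would largely miss a steeper dose response under pembrolizumab. The documents do not support that: no objective or hypothesis mentions dose-by-arm, no SD or effect size is given, and the loss depends on the assumptions in step 5. A reader might also infer that all band values would be pooled as if independent, which would inflate the type I error (26% to 44% across the simulated settings). Section 8.4 does not state that analysis and speaks of comparison within patients.

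A slope analysis has limits of its own. It assumes a shape for the trend, and it misses an arm effect that is the same at every dose. It should therefore be added to the arm comparison and not replace it.

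**Conclusion.** The point holds as a mismatch between aim and test. Section 5.4.1 states a dose-injury aim, section 8.4 contains no dose term, and no other section supplies one. The handling of correlated regions within a patient is unspecified. This conclusion rests on the text alone.

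The numerical size is conditional. The 20% to 30% chance of a false positive applies only if arms are compared in eight bands without adjustment at correlations of 0.7 to 0.3, and it is lower with stronger correlation. No general claim about lost power for dose-by-arm is justified. The consequence is confined to an exploratory analysis; neither primary endpoint is affected.

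**What to change.** Add a dose analysis to section 8.4, done separately for HU and f_air:

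- For each patient i and region j, take the change from baseline Δᵢⱼ and a dose score dⱼ (band mid-dose or ordered band, fixed in advance). Fit one slope per patient, bᵢ = Σ(dⱼ − d̄)Δᵢⱼ / Σ(dⱼ − d̄)². Test the mean slope against zero and report it with a 95% confidence interval, overall and by arm.
- As an alternative, if it converges with 20 patients, use a linear mixed model with dose, arm and dose-by-arm terms and patient random effects.
- Keep an overall arm comparison, made on change from baseline with one value per patient.
- Label dose-by-arm as exploratory.
- Define the regions and use one number throughout, stating whether lung below 0.5 Gy is counted.

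The cost is SAP wording; no scan, visit or patient is added. There are two downsides. The shape of the dose trend has to be assumed. Patients treated in 3 and in 5 fractions (section 5.6.1.2, Table 2) share the same physical-dose bands although dose per fraction differs: at 36 Gy, 36/3 = 12 Gy against 36/5 = 7.2 Gy. The report should show the slopes by fractionation group as a description.

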8.5 Correlation between PET data and Blood and Tissue markers

The correlation between the continuous variable SUV and the categorical variables tissue PD-1 and PD-L1 IHC will be assessed with the ANOVA test. The correlation between the continuous SUV and blood variables will be assessed with the paired t-test.

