3.2 Secondary Objectives & Hypotheses

Objective 1:

To assess uptake (visual and quantitatively, expressed as SUV_{max} , SUV_{mean} and SUV_{peak}) of radiolabeled pembrolizumab (^{89}Zr -pembrolizumab) in the tumor and lymph nodes by use of PET.

Hypothesis 1:

^{89}Zr -pembrolizumab tumor uptake heterogeneity between patients is expected and can be visualized. We expect that the level of ^{89}Zr -Pembrolizumab uptake will be related to the immunohistological results (immune effector subsets with special interest to the expression of PD-1 and PD-L1) of the whole tumor as well as regional tumor areas.

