4.2.4 Rationale for Endpoints

This an exploratory study that aims to evaluate the safety of the trimodality approach and characterize the immunological mechanisms of action of combination radiotherapy and immunotherapy. Therefore the primary endpoints of this study are the tolerability and toxicity of combined SBRT +/- pembrolizumab treatment and surgery and to analyze the immunological antitumor response. The endpoints will be assessed by clinical signs of

radiation pneumonitis and examination of tumor core biopsies and resection material, FACS analysis on EBUS-FNA of TDLNs and peripheral blood to detect immunomodulation.

Secondary endpoints are the correlations of *in-vivo* PD-1 expression, quantified by immune-PET, with tissue and blood based immune-parameters.

The levels of PD-1 and PD-L1 expression are variable over time (see section 4.1.8) and expression has been found to be heterogeneous between and within tumor lesions of the same patient. The biomarker PD-L1 IHC is currently being validated in multiple clinical studies to stratify patients based on the intensity and percentage of positive staining. This trial is a unique opportunity to study the 3-dimensional uptake of ⁸⁹Zr-pembrolizumab in the tumor and correlate the imaging result with the 3D immunohistochemistry results of the surgical tumor specimen.

Although pneumonitis will be assessed as a symptom, an exploratory objective is to evaluate radiation induced changes to healthy lung tissue after SBRT +/- pembrolizumab treatment in the resected lung lobe.

The number of patients (n=10 in each arm) is too low to correlate study parameters to clinical outcome in terms of progression-free or overall survival.

4.2.5 ⁸⁹Zr-pembrolizumab imaging

To identify patients that will benefit the most from treatment with mAbs like pembrolizumab, better knowledge of the *in vivo* behavior of the drug is warranted. For this, positron emission tomography (PET) imaging with radiolabeled mAbs (immuno-PET) is an attractive option.

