5.3.2.4 Blood sample analysis

Blood samples (7 mL) will be withdrawn at 10 min post-injection, 72 hours and 144 hours post-injection of ^{89}Zr -pembrolizumab to determine ^{89}Zr -kinetics based on measurements of radioactivity.

5.3.2.5 ^{89}Zr -pembrolizumab PET procedure

All PET scans will be performed on a Philips Ingenuity TF PET/CT scanner.

All patients will undergo two whole body PET scans at $t = 72$ and $t = 144$ hours post-injection. The PET scans will be preceded by a 30 mAs low-dose CT, used for attenuation correction and anatomical localization of the PET-signal. Following CT, a total body PET scan will be acquired. PET scans consist of 10-12 bed positions, depending on the length of the patient, of 5 minutes each. Total acquisition time per scan, including low dose CT will be around 60 minutes.

PET data will be normalized and corrected for randoms, tissue attenuation, decay, scatter and dead time. PET-CT data will be reconstructed with TF-OSEM, resulting in a transaxial spatial resolution of ~ 7 mm in the centre of the field of view. Regions of interest (ROIs) will be defined using the CT images which are co-registered to the PET-CT data. ROIs around the organs which accumulate ^{89}Zr (e.g. liver, lung and other metastatic lesions) will be drawn manually directly on the PET images. All tissue concentrations will be related to the blood concentration (venous samples). The radioactivity concentrations in all regions for all imaging time points will be recorded digitally in a spread sheet.

Quantitative accuracy of ^{89}Zr -PET scans was previously confirmed in our center using phantom studies and comparisons between PET-derived and biopsy tumor radioactivity concentrations (64, 65).

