6.0 TRIAL FLOW CHART

6.1 Study Flow Chart

Trial period	Screening Phase	Imaging	Induction treatment phase	Surgery	Follow-up
Scheduling Window (Days)	-30 to -1	-14 to 0	From day 1 to day 56 (2 weeks after 2 nd pembrolizumab cycle)	From day 56 to day 70	From surgery to 6 months thereafter
Administrative Procedures					
Informed Consent	X				
Eligibility Criteria	X				
Demographics and Medical History	X				
Prior and Concomitant Medication Review	X				
PET Imaging					
⁸⁹ Zr-pembrolizumab		X ^a			
Clinical Procedures/Assessments					
Review Adverse Events	X		X ^b		
Full Physical Examination	X				
Directed Physical Examination	X		X ^b		X ^c
Vital Signs and Weight	X		X ^b		
ECOG Performance Status	X		X ^b		
12-lead ECG	X				
¹⁸ F-FDG PET-CT		X		X	
Laboratory Procedures/Assessments					
Pregnancy Test	X				
Complete Blood Count (CBC)	X	X ⁱ	X ^b		
Comprehensive Serum Chemistry Panel	X		X ^b		
Urinalysis	X				
T3, FT4 and TSH	X		X ^d		
Treatment					
SBRT			X		
Pembrolizumab			X ^a		
Surgery				X	
Efficacy Measurements					
Tumor Imaging (CT thorax +/- abdomen and MRI brain)		X	X ^e		X ^f
Tumor Tissue and Blood analysis					
Core tumor biopsy	X				
EBUS FACS		X	X ^g		
Surgical resection specimen				X	
Immunophenotyping		X ^h	X ^h	X ^h	X ^h

X^a: only for patients randomized to the SBRT + pembrolizumab arm; X^b: every cycle; every 6 weeks; X^c: if indicated; X^d: after 2nd pembrolizumab cycle; X^e: within 2 weeks of surgery; X^f: following resection every 3 months for the first 2 years and every 6 months for the 3 years thereafter; X^g:; X^g:between week 2 and 3 after SBRT; . X^h: see section 7.1.2.10 for timepoints; Xⁱ: 72 and 144 hours post-injection for patients undergoing ¹⁸F-FGD-PET-CT

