7.1.2.10 Immunophenotyping on peripheral blood

To evaluate the pre- and on-treatment immune status, polychromatic flowcytometric analyses of lymphoid and myeloid subsets in peripheral blood will be performed at t = 0, 21 days (immediately prior to 2nd therapeutic dose), just before surgery, one week after surgery and after 6 months. Heparinized blood (40 ml) will be taken at each of these time points and PBMC isolated. The following 8-12 marker panels will be run on a BD LSRFortessa (with appropriate FMO controls): 1) Treg/effector T cell activation panel: CD3, CD4, CD8, CD25, CD127, CD45RA, Ki67, FoxP3, HLA-DR, CTLA-4, PD-1, CD27; 2) Dendritic cell panel:

CD1c/BDCA-1, CD202/BDCA-2, CD141/BDCA-3, M-DC8 (Sulph-LacNac), CD14, CD11c, CD16, CD19, CD40, CD80, PD-L1; 3) Myeloid-derived suppressor cell panel: CD11b, CD14, CD33, CD3/19/56 (Lin), HLA-DR, CD15, CD16, PD-L1. By performing these analyses at the indicated time points, we will gain unique insight in the kinetics of T cell activation following SBRT and PD-1 blockade and pre-, on- and post-treatment immune effector/suppressor subset profiles that may show differences between the two treatment arms, as we previously showed in a trial of combined ipilimumab and Prostate GVAX immunotherapy (76-78).

7.1.2.11 Ultrasound endoscopy guided cytological lymph node aspiration for immunological cell composition (EBUS FACS)

Patients will undergo an EBUS-FNA of the ipsilateral and contralateral hilar and mediastinal lymph nodes within 2 weeks before and between week 2 and 3 after SBRT (see section 5.4).

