8.2.2 Immunophenotyping in peripheral blood

All parameters will be quantified on a linear scale and compared within each patient (baseline vs on-treatment vs post-induction vs post-surgery) and between the treatment arms (SBRT vs SBRT + pembrolizumab) with the use of the paired t-test and the independent samples t-test, respectively.

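### Section 8.5 assigns a paired t-test to the SUV–blood correlation; that test compares two means and cannot measure association

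*Combined protocol and SAP*

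**What the plan says.** Section 8.5 deals with PET against tissue and blood markers. SUV against tissue PD-1 and PD-L1 staining, treated as categorical, is to be analysed by ANOVA. For blood it says: "The correlation between the continuous SUV and blood variables will be assessed with the paired t-test".

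Section 4.2.4 gives the endpoint its status. The secondary endpoints are there described as correlations of in-vivo "PD-1 expression, quantified by immune-PET, with tissue and blood based immune-parameters". The formal secondary hypothesis in Section 3.2 is narrower: it expects that "uptake will be related to the immunohistological results" and does not mention blood.

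Elsewhere the plan uses the paired t-test to compare one quantity with itself over time:
- Section 8.4, CT density: "Baseline and post induction treatment values within patients will be assessed by the paired t-test".
- Section 8.2.2, blood immunophenotyping: "All parameters will be quantified on a linear scale and compared within each patient", from baseline through to after surgery.
- Section 8.2.3, lymph node cells: post-induction against baseline.

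Section 8 names no correlation coefficient or regression. The flow chart in Section 6.1 marks the ⁸⁹Zr-pembrolizumab PET as "only for patients randomized to the SBRT + pembrolizumab arm". With 10 patients per arm (Section 5.2), that gives about 10 SUV–blood pairs.

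**The concern.** The stated aim is a correlation, but the named test addresses a different question. In Sections 8.2.2, 8.2.3 and 8.4 the paired difference has a meaning because both members of the pair are the same measurement. In Section 8.5 the two members are different quantities, and their mean difference says nothing about whether they vary together.

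Section 8.5 does not define its blood variables. The wording of Section 4.2.4 points to the flow-cytometry subsets of Section 7.1.2.10. Their units are not stated, since Section 8.2.2 mentions only a linear scale, so on that reading the result depends mainly on the scale in which a marker is recorded. The other possible reading is ⁸⁹Zr radioactivity in blood (Sections 5.3.2.4 and 5.3.2.5). The units could then be made to match, but the test would still only compare average tumor uptake with average blood activity.

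Followed as written, the analysis could report a significant correlation where none exists, or miss a strong one.

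**Working it through.** The plan gives no figure for this analysis, so there is none to reproduce. The check is of what the named test responds to.

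**Inputs.** From the documents: n = 10 pairs (Sections 5.2 and 6.1). Assumed, because the documents give none: two-sided 5% level, bivariate normal data, tumor SUV 6±2, and several blood-variable means and SDs.

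**Formula.** With SUV mean and SD m₁, s₁, blood mean and SD m₂, s₂, and correlation r:

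- s_d = √(s₁² + s₂² − 2·r·s₁·s₂)
- t = (m₁ − m₂) / (s_d/√n)

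The correlation enters only through s_d, the yardstick for the mean difference. If m₁ = m₂, the rejection rate is 5% whatever r is. If m₁ and m₂ are far apart, the test rejects whatever r is.

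**Effect of units** (sample values fixed, n = 10). The same marker is recorded in three ways.

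| Marker recorded as | s_d at r = 0.90 | t at r = 0.90 | t at r = 0 |
|---|---|---|---|
| Percentage, 30±8 | √(4 + 64 − 28.8) = 6.26 | −24/(6.26/√10) = −12.1 (p = 7×10⁻⁷) | −9.2 |
| Fraction, 0.30±0.08 | √(4 + 0.0064 − 0.288) = 1.93 | 5.7/(1.93/√10) = +9.3 (p = 6×10⁻⁶) | +9.0 |
| Percentage divided by 5, 6±1.6 | √(4 + 2.56 − 5.76) = 0.89 | 0 (p = 1) | 0 |

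The correlation is identical in all three rows. The sign and significance of t are set by the units, and they are nearly the same at r = 0 as at r = 0.90.

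**Rejection rates of the paired t-test** (simulation, 100,000 runs per cell, agreeing with the exact noncentral t).

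| Blood variable | r = 0 | r = 0.5 | r = 0.9 | r = −0.9 |
|---|---|---|---|---|
| Cell subset 30±8 | 100% | 100% | 100% | 100% |
| Cell subset 7.5±2 | 32% | 56% | 99.7% | 19% |
| Equal mean and SD, 6±2 | 5% | 5% | 5% | 5% |
| Blood radioactivity in SUV units, 5±1 | 24% | 37% | 66% | 16% |
| Blood radioactivity in SUV units, 3±0.6 | 98% | 99.7% | >99.9% | 91% |

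In every row Pearson's test rejects in about 5%, 33% and 98% at r = 0, 0.5 and 0.9, and Spearman's in about 5%, 26% and 94%. Both have the same power at r = −0.9 as at 0.9. The paired t-test treats equally strong positive and negative associations differently.

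**What a correct method delivers at n = 10.** The interval for Spearman's rho uses Fisher's z with variance (1 + ρ²/2)/(n − 3).

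- Observed 0.5: z = 0.549, SE = √(1.125/7) = 0.401, 95% CI about −0.23 to 0.87.
- Observed 0.7: z = 0.867, SE = √(1.245/7) = 0.422, 95% CI about 0.04 to 0.93.

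**The case against.** The strongest reply concerns weight. The trial is exploratory, with no power calculation (Section 5.2). Section 3.2 does not name blood, so the endpoint status rests on a sentence in a rationale section. The primary endpoints are untouched, and imaging does not guide treatment (Section 10.3.2). The sentence itself says correlation, so the intent is clear and an analyst might simply substitute the right test. With about 10 pairs the right test recovers little: power at a true r of 0.5 is about 33% with Pearson and 26% with Spearman. The rejection rates rest on assumed means and SDs, and the blood-radioactivity reading is the less likely one.

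Most of this stands as a limit on severity. The tabulated rates illustrate the principle and do not estimate this trial's error rate; the argument from the formula and the units does not need them. None of it makes the paired t-test valid. Small size and exploratory status argue for an estimate with an honest interval. A silent correction at analysis would also leave a choice, made after the data are seen, among three SUV metrics (Section 5.3.2.6), two scans (Section 5.3.2.5) and five blood time points (Section 7.1.2.10).

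It is fair that the unspecified metric, scan and time point are a separate and lesser matter. They affect the ANOVA half of Section 8.5 too. Because the PET precedes treatment, the baseline blood sample is the natural partner.

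**Conclusion.** The concern holds. Section 8.5 names a test that does not address the correlation it is assigned to, and no other section supplies a method. Applied literally, the result follows the difference in means and the choice of units: in the assumed examples it ranges from 5% rejection at r = 0.9 to 100% rejection at r = 0. That the test does not measure association needs no assumption; the percentages depend on the assumed means, SDs, normality, 5% level and n = 10.

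The scope is narrow. It covers the blood part of the secondary endpoints in Section 4.2.4. The tissue part uses ANOVA, which does test association. The consequence is a misreported exploratory result, with no effect on patient safety or sample size. It should be fixed before analysis.

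**What to change.** Replace the last sentence of Section 8.5 with: *The association between SUV and each blood variable will be described with Spearman's rho (or Pearson's r on log values) with a 95% confidence interval, as exploratory results.*

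Before analysis, the study team should:
- state what the blood variables are;
- choose one of the two coefficients (Spearman is simpler, since logs fail for a subset frequency of zero);
- name the main SUV metric, scan (72 or 144 hours) and blood time point;
- report all other pairings as supportive, drawing no claim from the largest.

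The cost is SAP wording only; no extra data or procedures are needed. The drawbacks are wide intervals with about 10 scanned patients and, if the data are normal, slightly less power for Spearman than for Pearson (about 94% against 98% at r = 0.9).
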